## 2. STUDY OBJECTIVES

### Primary objective:

- Confirm operational robustness and technical reliability of the software when operating in real-time in an operational ICU environment. We will measure indicators of system reliability and availability (e.g. what percentage of time is the system available, at different times of the day and night, on weekdays versus weekends, etc.) and the lag of the system (e.g. delay between data recorded at the bedside and model producing an output).

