## 3. STUDY DESIGN

This study is a prospective multi-centre observational study that will include four intensive care units from two different NHS Trusts.

The duration of the study will be up to 24 months.

We will include 100 to 300 adult patients with early sepsis in ICU (within 24h of ICU admission). This number is a pragmatic, realistic estimate of how many patients will satisfy the inclusion criteria in the study period (assuming a conservative 60 admissions per month on each unit (reality is closer to 80-100 pre-COVID-19), and 20% sepsis at admission), and will allow us to deliver on the study objectives.

With regards to human assessors, we will include 6 to 15 ICU doctors, mixing senior registrars, ICU fellows and consultants.

The “system” will be a purpose built webapp accessed from a dedicated laptop, connected to an NHS ICT server, with secure login. It will be linked to a duplicate of the Philips ICCA database (Imperial College Healthcare NHS Trust) or the EPIC EHR (UCLH) which contains ICU patient data in near real time (estimated lag of 5 to 15

minutes). The system will be running the AI Clinician algorithm, which processes ICU patient data and outputs a suggested dose of intravenous fluids and vasopressors. Four times a day (every 6 hours), the system analyses newly admitted ICU patients and identify those who fulfil the sepsis-3 criteria. If they do, they will be added to a list of patients for potential inclusion that will be accessible from within the software (and assessed by human evaluator for enrolment).

The system will contain several tabs:

- 1- **Patient screening.** It displays a list of patients screened and highlighted by the system as fulfilling sepsis-3 criteria. The user (human evaluator) has the option to include them into the study, after verification of the inclusion/exclusion criteria (see sections 4.2 and 4.3 for these criteria).
- 2- **Individual patient data.** This screen contains a drop-down list of patients included in the study. After selecting one, the data time series of this individual patient are displayed here, along with the doses of fluids and vasopressors actually given by human “on-duty” doctors and nurses.

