- 3- **Evaluation tab.** This is where the evaluation of the AI and human doctors’ decisions takes place. The option to scroll through the various previous time points is provided. The evaluation by the human evaluator takes place in several subsequent steps: First, the human evaluator makes a recommendation based on patient data alone (data point #1). Then, the human evaluator is presented with the AI recommendation (data point #2), along with other information (confidence in the suggested decision, explanation of why this action was recommended). They “rate” the AI decisions, by classifying the AI suggested actions in different categories, such as “likely safe”, “likely inappropriate”, “possible too low”, or “possibly too high”. Finally, the human evaluator is presented with the actual decision (made by human clinicians, data point #3) and the subsequent patient evolution (at least a few hours, but the final outcome of ICU death or survival will be presented if available). The human evaluators rate the actual decisions using the same scale, e.g. “likely safe”, “likely inappropriate”, etc. There will be a free-text box to enable the user to provide feedback on their decisions.

The software will be accessed on the dedicated laptop from within the NHS hospitals by off-duty clinicians enrolled in the study, whom we call “human evaluators”. To explore system’s usability around the clock, there will be no restrictions with regards to timing of the research, so the human evaluators will be able to conduct the research at any time and on any day of the week.

We intend to conduct the study during 1-hour sessions, during which the users will conduct these 2 actions:

- 1) Identify new patients for inclusion from a pre-screened list
- 2) Assess multiple decisions made on multiple included patients. Based on a conservative number of 5 patients with sepsis on each unit at any point in time, and between 4 - 10 sessions per user, we will gather a maximum of 600 to 1,500 data points (100 data points per user for 6 to 15 users). We expect to include an estimated

100 to 300 separate patients across 4 sites (based on 20 patients per month per unit and 27 months of total study period over the 4 units, which gives 540 potential eligible patients). This will enable to complete the study objectives.

Data about the system's operational reliability will be automatically collected:

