### 3.1. STUDY OUTCOME MEASURES

Data of interest	Study outcome measures
System / usability data	Data availability: what percentage of essential and optional data fields are available 24/7. System availability: delay in generating response 24/7. Number and nature of technical issues (drop-outs, freezes).
Anonymised patients' data	Patient demographics (age in years, gender, primary diagnosis) Outcomes: organ function (hourly SOFA), ICU and hospital mortality
Bedside physicians' data	Doses administered to patients of intravenous fluids and vasopressors, which are action chosen by on-duty clinicians
Evaluators' data (the doctors assessing the AI in the background)	Evaluator's grade and seniority A custom-made interface linked to a database will capture and record the following: 
 
- What dose they would recommend, before and after seeing the AI suggested dose.
 
- Agreement with AI suggested dose: does it appear appropriate, too high or too low?
 

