## 7. STATISTICS AND DATA ANALYSIS

Data and all appropriate documentation will be stored for a minimum of 10 years after the completion of the study, including the follow-up period.

Data of interest	Statistical analyses
-------------------------	-----------------------------

System / usability data	Simple descriptive statistics (e.g. average system lag, number of technical issues per week...)
Anonymised patients' data	Simple descriptive statistics of the patient characteristics. Comparison of the training and prospective cohorts (simple parametric and non-parametric tests comparing demographics, severity of illness, etc).
Evaluators' data (the doctors assessing the AI in the background)	Descriptive statistics from evaluators data: Agreement between initial human evaluator doses (data point #1) and AI decisions (data point #2), and between AI decisions (data point #2) and actual doses given to patients (data point #3). Proportion of AI decisions (data point #2) classified as appropriate / possibly too low / possibly too high Proportion of human decisions (data point #3) classified as appropriate / possibly too low / possibly too high
AI decisions evaluation	Quantitative analyses of AI decisions: estimate patients' outcomes if the AI decisions were followed and compare them to actual outcomes (which were linked with human decisions). We will use 2 methods: 1) compare short-term outcomes between model-concordant treatment and model-non-concordant treatment, with confounder adjustment; 2) off-policy policy evaluation of the AI policy in the prospective ICHT cohort.

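### The primary objective defines lag as ending at model output, but the listed automatic logs stop at the database and the server, so slow or missing output is seen only in 24 to 150 self-timed sessions

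*Protocol*

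**What the plan says.** Section 2 (primary objective) names two things to measure. One is availability: "what percentage of time is the system available, at different times of the day and night, on weekdays versus weekends". The other is lag, given as the "delay between data recorded at the bedside and model producing an output". Section 3.1 turns these into outcome measures: availability of essential and optional data fields and delay in generating a response, both 24/7, and the number and nature of technical issues such as drop-outs and freezes.

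Section 3 lists three items collected automatically: the time from a clinical event to its record in the database, the date and time of every system access, and server status with down-time and outages. Technical issues met by users go on a separate online form.

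On exposure, Section 3 says "we will include 6 to 15 ICU doctors", with "between 4 - 10 sessions per user" and sessions of one hour. To explore usability around the clock, it says that "there will be no restrictions with regards to timing of the research". Section 7 plans simple descriptive statistics for the system data, with "average system lag, number of technical issues per week" as examples.

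**The concern.** The lag defined in Section 2 runs from the bedside to the model's output. The lag logged in Section 3 ends when the record reaches the database, before the algorithm has produced anything. No listed log shows whether or when an output was returned, and none records an application freeze while the server is up. For these the only listed source is the user.

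Users are off-duty doctors who choose their own hours. Permission to log in at night or at weekends does not produce sessions then. A count of their reports per week also depends on how often they log in as well as on how often the system fails.

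At stake is part of the primary objective. A running server with a stalled algorithm is a failure that a study of technical reliability should detect, and Section 1.1 describes a later stage in which recommendations are displayed to clinicians.

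**Working it through.** **1. What is measured, side by side**

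| Quantity wanted (Sections 2 and 3.1) | Automatic record listed in Section 3 |
|---|---|
| Availability by day/night, weekday/weekend | Yes for the server: status, down-time, outages |
| Lag, bedside record to database | Yes: event-to-record time |
| Lag, database to model output | None listed |
| Model returned no output | None listed |
| Freezes and other application faults with the server up | None listed; user form only |

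**2. The plan's own figures.** Section 3 gives 100 data points per user for 6 to 15 users: 6 × 100 = 600 and 15 × 100 = 1,500, as printed. It also gives 20 patients per month × 27 unit-months = 540, as printed. The inputs are therefore read as intended.

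**3. Hours of user observation.** The protocol does not print a session total. Its inputs give users × sessions: 6 × 4 = 24 and 15 × 10 = 150, each of one hour.

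**4. Share of running time.** A month is 365.25 × 24 / 12 = 730.5 h.
- 27 unit-months: 27 × 730.5 = 19,724 h. Coverage is 24/19,724 = 0.12% to 150/19,724 = 0.76%.
- 24 calendar months (the maximum duration): 17,532 h. Coverage is 0.14% to 0.86%.

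The first line counts each session as one unit-hour. If every session counted for all four units, its upper end would be 4 × 0.76% = 3.0%.

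**5. What a weekly count would show.** Assume one report per failed session. Issues per week = sessions × proportion failing / weeks.

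| Sessions failing | Per session | Per week, 27 unit-months (117.4 weeks) | Per week, 24 calendar months (104.4 weeks) |
|---|---|---|---|
| 50% | 12/24 to 75/150 = 50% | 0.10 to 0.64 | 0.11 to 0.72 |
| 100% | 24/24 to 150/150 = 100% | 0.20 to 1.28 | 0.23 to 1.44 |

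If all four units ran at the same time (27/4 = 6.75 months, about 29.3 weeks), a fault in every session would read as 24/29.3 = 0.8 to 150/29.3 = 5.1 per week. The weekly figure moves with the exposure basis and the number of logins. The per-session figure does not.

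**6. Night sessions.** The night share is not in the protocol, so 5% to 33% is assumed. Take a true night fault rate of 30%, again as an illustration. The chance of seeing no fault in m night sessions is 0.7^m.
- 24 sessions: m = 1 to 8, chance 0.70 to 0.06.
- 150 sessions: m = 8 to 50, chance 0.06 to nearly 0.

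The blind spot is serious at the low end of the planned range or with few night sessions. It is small at the high end with good spread.

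**The case against.** A reader might infer that technical faults are seen only in sessions and that a badly failing system would look sound. The documents do not support that. Server status, down-time and outages are logged whether or not anyone is logged in, so server availability can be broken down by hour and by weekday, and a server that is often down would show. The data-feed part of the lag is also time-stamped automatically. This objection stands, and it confines the point to model output and application-level faults.

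Session-only observation of response delay is inferred from a list. Section 3.1 states a 24/7 intent, the system already screens every 6 hours, and evaluators can scroll back to earlier time points. But intent is not a data source. The protocol does not say whether the outputs shown for earlier time points were generated live or on request, so reviewing a night-time decision by day does not show that the system worked that night.

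The weekly count is only an example, and the access log already offers a denominator. That is right: the weekly rate is not a fixed analysis, and a statistical analysis plan (not shown) could choose a better one. It could also add the day/night breakdown. It could not analyse data that the protocol does not list for collection.

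A reader might also cross the two contrasts and judge the plan on weekend nights alone. The objective names "at different times of the day and night, on weekdays versus weekends" as separate contrasts and does not require that small cell, so no limit is drawn from it here.

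**Conclusion.** The point holds in a narrow form. Sections 2 and 3.1 ask for lag to model output and for response delay around the clock. The automatic collection in Section 3 does not list the data that would give either. As listed, slow or missing output and application faults on a running server rest on user reports from 24 to 150 self-timed hours, about 0.1% to 0.8% of the 27 unit-months, with no assured night or weekend cover.

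This rests on three assumptions: the list in Section 3 is complete, each session counts as one unit-hour, and the planned numbers of users and sessions are met. If model outputs and their times are in fact stored automatically, the remedy is only to say so. The server-availability half of the primary objective is not affected. The change is a cheap and worthwhile improvement; the gap does not show that the whole primary objective fails.

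**What to change.** **Section 3, automatic collection.** Add a scheduled model run for included patients at fixed times around the clock, at least with each existing 6-hourly screening run. For each run, record whether an output was returned, the time from the latest bedside record to the output, and whether essential fields were present. Use the scheduled times as denominator, so that a run leaving no record counts as no output. Report lag and output availability by day/night and weekday/weekend from this log.

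At four runs a day, 27 unit-months (27 × 365.25/12 = 822 unit-days) would give up to 822 × 4 = 3,288 scheduled times, of which about 2/7, or 939, fall at weekends. Times when a unit has no included patient reduce this.

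**Section 7, system and usability data.** Report user-reported issues per session or login attempt, with the access log as denominator. Keep outages as a percentage of time from the server log, since outages between sessions have no session denominator.

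**Cost.** A scheduled script on a system that already runs every 6 hours, some log storage, and reliability figures that may look less favourable.

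### No rule fixes which patients and time points evaluators rate, so the proportions of AI and human decisions rated appropriate describe an undefined, possibly selective set

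*Protocol*

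**What the plan says.** The relevant text is in Section 3 (Study design) and Section 7 (Statistics and data analysis) of the protocol.

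- **Inclusion.** Patients who meet sepsis-3 appear on a screening list. "The user (human evaluator) has the option to include them into the study, after verification of the inclusion/exclusion criteria".
- **Reaching a patient (tab 2).** "This screen contains a drop-down list of patients included in the study. After selecting one, the data time series of this individual patient are displayed", and the doses given by the on-duty team are shown alongside.
- **Reaching a time point (tab 3, Evaluation).** "The option to scroll through the various previous time points is provided".
- **Order of rating.** The evaluator first records their own recommendation from patient data, then sees and rates the AI suggestion, then sees and rates the actual decision.
- **Sessions.** "We intend to conduct the study during 1-hour sessions", and "the human evaluators will be able to conduct the research at any time and on any day of the week". Within a session, the only instruction on what to rate is "Assess multiple decisions made on multiple included patients".
- **Output.** Section 7 plans the "Proportion of AI decisions (data point #2) classified as appropriate / possibly too low / possibly too high", and the same for human decisions.

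The 6-hourly schedule in Section 3 governs screening for sepsis-3. It does not say which decisions are rated.

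**The concern.** A proportion needs a denominator. Section 7 words its output as a proportion of AI decisions, which a reader will take to mean the decisions the system produced for the included patients. Under Section 3 the denominator is whatever time points were opened. The protocol has no random or consecutive order, no assignment of patients or time points to evaluators, no fixed time point and no quota per patient.

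Hypothesis 2 in Section 1.2 and the first secondary objective in Section 2 depend on these ratings. Section 1.1 also describes a later stage in which recommendations are shown to clinicians, so the figure is likely to be used. If evaluators favour unstable periods, or simple ones, the reported share shifts, and collecting more ratings does not remove the shift. The choice is made while data are collected, so an SAP written later cannot supply a sampling frame that was never applied.

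**Working it through.** **1. The plan's own count.** Section 3 gives 6 to 15 users with 100 data points each: 6 × 100 = 600 and 15 × 100 = 1,500. This matches the stated maximum of 600 to 1,500. I take one data point here as one rated time point.

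**2. Room for choice within a session.** The count is "Based on a conservative number of 5 patients with sepsis on each unit at any point in time, and between 4 - 10 sessions per user". For 100 ratings per user:

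- 100/10 = 10 to 100/4 = 25 ratings per session
- over 5 patients on one unit, 10/5 = 2 to 25/5 = 5 ratings per patient

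An evaluator could therefore cover every current patient on a unit. The main freedom left is which time points to rate.

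**3. Share of decisions rated.** The protocol gives neither the decision interval nor the length of stay evaluated, so both are assumptions. Decisions = patients × days × 24 / interval in hours.

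| Patients | Days | Interval (h) | Decisions | 600 ratings | 1,500 ratings |
|---|---|---|---|---|---|
| 300 | 3 | 1 | 21,600 | 3% | 7% |
| 300 | 3 | 4 | 5,400 | 11% | 28% |
| 100 | 3 | 4 | 1,800 | 33% | 83% |
| 100 | 1 | 6 | 400 | all | all |

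These figures assume that no decision is rated twice. Coverage could be anything from a few percent to complete.

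**4. Size of a selection effect.** Assume a true appropriate share of 0.80.

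*Direct selection.* If inappropriate decisions are opened r times as often as appropriate ones, the reported share is 0.8/(0.8 + 0.2r).

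- r = 2: 0.8/1.2 = 66.7% (−13.3 points)
- r = 1.5: 0.8/1.1 = 72.7% (−7.3)
- r = 1/1.5: 0.8/0.933 = 85.7% (+5.7)
- r = 0.5: 0.8/0.9 = 88.9% (+8.9)

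*Selection through patient state.* Assume half the time points are unstable, with 70% of AI decisions appropriate there and 90% elsewhere. The true share is 0.5 × 0.70 + 0.5 × 0.90 = 80%.

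- Unstable points opened twice as often: (2/3) × 0.70 + (1/3) × 0.90 = 76.7% (−3.3)
- Unstable points opened half as often: (1/3) × 0.70 + (2/3) × 0.90 = 83.3% (+3.3)

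**5. Comparison with random error.** The 95% half-width is 1.96 × √(0.8 × 0.2/n), which is 3.2 points at n = 600 and 2.0 at n = 1,500. This treats ratings as independent. Ratings that cluster within patients and evaluators would usually make it wider.

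**The case against.** **Free choice is inferred.** No sentence says that evaluators pick their cases. The drop-down list belongs to tab 2, while rating takes place in tab 3, whose text does not say how a case is loaded. Scrolling may be meant only for viewing history, and an assignment rule could sit in evaluator instructions or the software specification. This stands, so a reader should not infer that the protocol instructs convenience sampling. The point is narrower: the workflow as described leaves the choice open, and nothing in the protocol closes it.

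**Selection on AI quality is indirect.** The AI suggestion appears only after the evaluator has recorded a recommendation, so an evaluator can hardly seek out poor AI suggestions in advance. This stands and favours the smaller shift in step 4. It is weaker for human decisions, because tab 2 shows the actual doses before rating.

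**The rated set need not be a minority.** This stands. At one decision per 4 hours for 3 days, coverage runs from 11% to 83% across the plan's own ranges of patients and ratings.

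**Later analysis can help.** Patient time series and doses are held, so rated and unrated time points can be compared and reweighted on recorded features. This stands in part, because an evaluator's unrecorded reasons for opening a time point cannot be adjusted for.

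**The output is secondary.** The primary objective rests on automatically collected reliability data and is untouched. The ratings are descriptive, with no test or threshold. AI and actual decisions are rated at the same time points, so their contrast is paired. All of this stands and limits the importance of the point, but each proportion, and the contrast, still describes only the time points opened.

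**Conclusion.** The point holds in a limited form. As Section 3 is written, the proportions in Section 7 come from an undefined and possibly selective set of time points. Selection would act mainly through patient state and, for human decisions, also through the doses visible in tab 2.

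Its direction and size cannot be derived from the protocol. The illustrations run from about 3 points to about 13, all on an assumed true share of 80% and assumed selection ratios. The upper figure needs selection directly on appropriateness and is a bound for illustration. Even the lower figure is as large as the nominal half-width of 2.0 to 3.2 points.

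A reader might go further and conclude that the estimate is certainly biased, that only a minority of decisions will be rated, or that no later analysis could help. The protocol supports none of these. The change is worth making before ratings begin, because the set of rated decisions cannot be redrawn once the sessions are over.

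**What to change.** **Section 3.** State that the software assigns the patient and time point for each rating, by random draw within patient or by a fixed consecutive rule. Keep scrolling for viewing history only. Log every assigned case that is skipped.

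**Section 7.** Report the number of decisions available and the number rated, and weight the proportions by the sampling fraction. For patient i with Nᵢ decisions available and nᵢ rated, each rating carries weight Nᵢ/nᵢ. This needs at least one rating per included patient. On the plan's figures the average lies between 600/300 = 2 and 1,500/100 = 15. If some patients cannot be covered, draw patients at random too and include that probability in the weight.

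**Inclusion.** A draw from included patients does not remove selection at entry, because inclusion is the evaluator's option. Report how many screened, eligible patients were not included.

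**Cost.** A small change to the evaluation tab of a purpose-built tool, and short additions to Sections 3 and 7. No extra sessions or patients are needed. Evaluators lose the freedom to pick cases.

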- Time elapsed between a clinical event (e.g., administration of a fluid bolus) and the record appearing in the database. This exploits the property of some clinical events to be time-stamped to quantify the lag in the system.
- Date and time of all system accesses
- Server status, down-time events, planned and unplanned outages. These events can be monitored remotely and logged by the ICT team.

An independent online form (survey-type) will be created to log all technical issues that the users may encounter (e.g., system unavailable, login issues etc). This survey will be kept separate from the system, so it can't be affected by server outage for example.

The data about the system's operational reliability and the technical issues reports do not contain patient sensitive information and will be available to researchers at Imperial College London, in the research groups of [name] and [name].

After running the study for 3 months on each study site, an interim analysis will be performed to test the data quality. A pseudo-anonymised dataset including the fields described in section 3.1 "study outcome measures" of all patients included so far in the study will be created. All patient identifiable information will be removed, patient NHS number will be replaced by an ad-hoc random number, and the mapping between the patients' true identity and identifiers will be kept on the NHS server. No patient health records will leave NHS systems.

The final analysis will occur at the end of the study period (after month 18, in August 2022), once all data has been collected. The pseudo-anonymised dataset will be transferred encrypted to an Imperial College London secured server, within the [name] Lab. Researchers in [name] and [name] groups will then conduct various modelling and analyses to assess the AI suggested decisions.

This trial will be conducted across four intensive care units: Imperial College Healthcare Trust - Charing Cross Hospital, Hammersmith Hospital, St Marys Hospital and University College London Hospital. All four units are capable of treating critically ill patients.

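### The lag interval that is collected runs between different points from the lag named in the primary objective, so the lag result may be too high or too low

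*Protocol*

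**What the plan says.** The protocol describes lag in four places.

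- **Section 2, primary objective.** Lag is a named indicator, with the example "delay between data recorded at the bedside and model producing an output". The clock starts at entry and stops at model output.
- **Section 3, data collected automatically.** The interval is "Time elapsed between a clinical event (e.g., administration of a fluid bolus) and the record appearing in the database". Its purpose follows: "This exploits the property of some clinical events to be time-stamped to quantify the lag in the system". The clock starts at the event and stops at the database.
- **Section 3.1, outcome table.** The measure is "System availability: delay in generating response 24/7". No start point is given.
- **Section 7, analysis table.** The summary is descriptive: "Simple descriptive statistics (e.g. average system lag, number of technical issues per week". No threshold or test is attached.

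The only lag figure is in section 3, where the linked record system is said to hold data in "near real time (estimated lag of 5 to 15" minutes. Neither section 3 nor the field list in Appendix 2 names the time at which an entry was saved.

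**The concern.** Operational robustness and technical reliability form the only primary objective, and lag is one of its named indicators. The figure reported should therefore belong to the software. As section 3 is worded, the interval begins when something happens to the patient. If staff enter that event later, their delay becomes part of the system's lag. The interval also ends before the model has run, so the one step that is wholly the software's own is missing.

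A sound data feed could then look slow because of charting practice, or a slow model could look fast because its run time was never counted. The four units also use two different record systems, so a difference in charting practice could be read as a difference between platforms.

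This concerns which time stamps are captured, not how they are summarised. If the entry time is not extracted, a later analysis plan may be unable to separate the parts.

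**Working it through.** No figure in the protocol can be rebuilt here: the 5 to 15 min is a planning estimate without inputs. The check is interval arithmetic.

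**Components**

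- *c* = charting delay, from event to entry saved. Not in the protocol; assumed 0 to 30 min.
- *L* = feed lag, from entry saved to visible in the database. The 5 to 15 min of section 3 is read this way; the protocol does not state its start point.
- *m* = model time, from visible in the database to output. Not in the protocol; assumed 0 to 5 min.

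**The two definitions**

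- Interval collected (section 3): *c* + *L*
- Lag named in the objective (section 2): *L* + *m*
- Error: (*c* + *L*) − (*L* + *m*) = *c* − *m*

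*L* cancels, so the sign of the error depends only on the two quantities that the protocol does not give.

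**Two invented cases**

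- A bolus is given at 10:00, entered at 10:30, visible at 10:40, and the model output appears at 10:45. Collected: 40 min. Objective: 15 min. Error: 30 − 5 = +25 min.
- An automatically stamped event occurs at 10:00, is visible at 10:10, and the output appears at 10:15. Collected: 10 min. Objective: 15 min. Error: 0 − 5 = −5 min.

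**Inflation of the feed lag alone, (*c* + *L*)/*L***

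| Assumed *c* (min) | *L* = 5 | *L* = 10 | *L* = 15 |
|---|---|---|---|
| 0 | 1.0 | 1.0 | 1.0 |
| 5 | 2.0 | 1.5 | 1.33 |
| 10 | 3.0 | 2.0 | 1.67 |
| 15 | 4.0 | 2.5 | 2.0 |
| 30 | 7.0 | 4.0 | 3.0 |

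A threefold result needs a mean charting delay of 2*L*, that is 10 min at *L* = 5 and 30 min at *L* = 15. If only half of the events are entered 30 min late and the rest at once, the mean *c* is 0.5 × 30 = 15 min and the ratios of the mean are 4.0, 2.5 and 2.0.

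**Ratio to the objective's own lag, (*c* + *L*)/(*L* + *m*), with *m* assumed to be 5 min**

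| Assumed *c* (min) | *L* = 5 | *L* = 15 |
|---|---|---|
| 0 | 5/10 = 0.50 | 15/20 = 0.75 |
| 5 | 10/10 = 1.0 | 20/20 = 1.0 |
| 30 | 35/10 = 3.5 | 45/20 = 2.25 |

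The same definition halves the lag in one corner of this table and more than triples it in another. Agreement in the middle row is a coincidence of *c* = *m*, not evidence that the measure is right.

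**The case against.** The strongest reply is that the protocol does not say that charting is late, or even that charting is involved. Section 3 limits the measure to some events that carry a time stamp, and does not say whether the stamp is a device time, a time typed by staff or the time of entry. With device or entry stamps, *c* drops out. This stands as a limit on size. It does not remove the conflict: the one example is a bolus being given, nothing restricts the measure to automatic stamps, and if entry times are meant, the text should say so. Model time is missing in every case.

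Second, the delay from event to record matters in its own right. Section 1.2 hypothesises acceptable, near real-time lag at the bedside, and a model that has not yet seen a bolus works without it whatever the cause. This also stands. The fault lies in calling the whole interval system lag, not in collecting it.

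Third, the objective's definition is only an example, section 3.1 names a further delay measure, and lag is purely descriptive. So no formal decision changes, and the section 3 interval is not shown to be the only lag result. But section 3 gives that interval the task of quantifying lag, and three descriptions that do not agree leave the primary indicator undefined.

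A reader might go further and infer that night and weekend comparisons of lag will show staffing patterns. The protocol does not support this. In section 2 the contrasts by time of day and day of week are attached to system availability; the lag example carries none.

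**Conclusion.** The point holds as a mismatch of definitions. The interval collected is not the lag that the primary objective names: it adds any delay before entry and omits the model step. The error is *c* − *m*, with either sign possible.

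The size is conditional. Under assumed charting delays of 5 to 30 min and the protocol's 5 to 15 min feed lag, the feed lag would look 1.3 to 7 times its value. With no charting delay and an assumed 5 min of model time, the objective's lag would be reported at 0.50 to 0.75 of its value. A reader might infer that the reported lag will be several times the truth. The protocol does not support that: it gives no charting delay, a 5 min delay yields only 1.33 to 2.0 for the feed lag, and the omitted model time pulls the other way.

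The correction is worth making because it concerns a primary indicator and depends on what is logged. No test or threshold is affected.

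**What to change.** - Reconcile sections 2, 3 and 3.1 on one definition of system lag, with stated start and end points.
- Log four times for each event, where the record systems keep them: event, entry saved, visible in the database, model output.
- Use entry saved to model output as the primary system lag. Stopping at the database would still leave the objective unmet.
- Report event to entry saved separately, as a descriptive charting delay. It bears on near real-time use at the bedside and should not be discarded.
- Where no entry time is kept, take system lag from automatically stamped records only, and report event-to-record delay for manually charted events under its own label.
- Give medians and upper percentiles beside the average, since a few very late entries can pull a mean up.

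The cost is a few sentences and one more time stamp from the record systems. Model-output time should come from the study software, and the response-delay measure in section 3.1 appears to need it already. The downside is fewer events in the system-lag summary where no entry time exists. Manually charted fluid boluses could be among those lost, which is why their event-to-record delay should still be shown.
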